9.10.3. Key Secondary Endpoints

As specified in the following sub-sections, multiple secondary endpoints will be analyzed using a mixed model for repeated measurements (MMRM) using the sandwich estimator to estimate the variance-covariance matrix. The dependent variable will be the change from baseline. Each of these models will include fixed effects for treatment group, timepoint, treatment group by timepoint interaction, stratification factor for region (U.S. versus non-U.S.), stratification factor for tumor location (lower limb vs. all other), and the baseline value of the corresponding endpoint. Statistical comparisons between treatment groups will be made at the specified timepoint. For the analysis of ROM only, tumor location will be replaced with joint type (knee, ankle, or other). An unstructured variance-covariance matrix will be used. If the unstructured variance-covariance matrix fails to converge, then alternative structures will be utilized. Statistical comparisons between treatment groups will be made based on a contrast statement at Week 25.

Analyses of the secondary endpoints described in the following sub-sections will be limited to data from Part 1 and will focus on comparisons between participants who received vimseltinib versus participants who received placebo during this period. The exception to this rule is for duration of response presented in Section 9.10.4.3.

These analyses may also be performed on the PP Set if the proportion of participants from the ITT Set who are excluded from PP Set exceeds 5%.

A separate analysis plan will describe the process for identifying the minimally clinical important difference (MCID) for PROMIS-PF, Worst Stiffness, and ROM. A responder analysis for each of these endpoints based on the MCID of each endpoint as determined by the analysis will be performed.

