5. SAMPLE SIZE DETERMINATION

The sample size selection of approximately 120 participants with TGCT (n~80 vimseltinib, n~40 placebo) was based on considerations for powering the analyses of the primary endpoint, key secondary endpoints, detection of rare safety events and overall exposure to vimseltinib, assuming 15% participant dropout. Participants will be randomized in a 2:1 ratio of vimseltinib versus placebo.

This sample size will have 98% power to detect a statistically significant difference between treatment groups, assuming true ORRs of 35% and 5% in the vimseltinib arm and the placebo arm, respectively, using a two-sided Fisher's exact test at a 5% type I error rate level.

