9. STATISTICAL CONSIDERATIONS

All analyses described in this plan are considered a priori analyses in that they have been defined prior to locking the database. All other analyses, if any, designed subsequently to locking the database, will be considered post hoc analyses and will be described as exploratory analyses in the clinical study report (CSR) or a separate document.

All summaries and statistical analysis will be performed using SAS v9.4 or higher.

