9.10.1. Multiplicity Control

To control overall type I error, a hierarchical testing procedure will be utilized. Statistical testing will be performed for the analysis of primary and key secondary endpoints in the following order at a 2-sided 0.05 alpha level for each:

- 1. ORR per RECIST v1.1 at Week 25
- 2. ORR per TVS at Week 25
- 3. Mean change from baseline in active ROM at Week 25
- 4. Mean change from baseline in the PROMIS-physical function score at Week 25
- 5. Mean change from baseline in the worst stiffness NRS score at Week 25
- 6. Mean change from baseline in EQ-VAS at Week 25
- 7. Proportion of responders based on BPI-30 (worst pain) NRS score and narcotic analgesic use at Week 25

If the primary endpoint is not statistically significantly different between treatment groups, the secondary endpoints will not be formally tested and nominal p-values will be provided. Contingent upon significance in the primary endpoint, each of the secondary efficacy endpoints will be tested sequentially in the order above. If any of the endpoints are not statistically significantly different between treatment groups, all subsequent endpoints will not be formally tested and nominal p-values will be provided.

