9.10.2. Primary Endpoint

Objective response rate (ORR) per RECIST v1.1 at Week 25 is defined as the proportion of participants with a CR or a PR as the Week 25 Tumor Response (as defined in Table 2) based on IRR per RECIST v1.1. ORR at Week 25 will be compared between the 2 treatment groups using a two-sided Cochran-Mantel-Haenszel (CMH) test stratified by the randomization stratification factors. The test will be performed at a 0.05 alpha level on the ITT Set. A 95% CI for the proportion in each arm using the Clopper-Pearson method as well as the difference in proportion and its associated Wald 95% CI will be presented. A Fisher's exact test and an exact 95% CI for the difference in proportion will be provided as a sensitivity analysis.

No confirmation (ie, CR or PR at the subsequent MRI assessment) will be required for a CR or PR per RECIST v1.1 as this is a randomized study. Complete and partial response will define response for the primary endpoint and additional efficacy analyses.

Determination of an overall response for each timepoint is based on the combination of responses for target lesions, and the presence or absence of one or more new lesions per RECIST v1.1. For this study, determination of the tumor response status for each participant in Part 1 with respect to the primary efficacy endpoint is shown in Table 2 below. All unscheduled assessments prior to Week 25 will be incorporated into the determination of ORR at Week 25 in a similar fashion as Week 13. End of Part 1 scans will be windowed according to Section 8.3. If a participant is missing a scan at Week 25, then they will be considered a non-responder.

Table 2: Definitions of Response for the Primary Efficacy Endpoint

Timepoint Response at Week 13	Timepoint Response at Week 25	End of Part 1 (Week 25) Tumor Response Status
		(Primary Efficacy Endpoint)
CR or PR	CR	Response (CR)
CR or PR	PD	Non-response (PD)
PR	Non-CR/non-PD/non-NE ^a	Response (PR) ^b
SD	CR or PR	Response (CR or PR)
SD	SD	Non-response (SD)
SD	PD	Non-response (PD) ^c
CR, PR, SD, and NE	NE	Non-response (NE)
PD	Any	Non-response (PD)
NE	CR or PR	Response (CR or PR)
NE	SD or PD	Non-response (SD or PD)

Abbreviations: CR=complete response; NE=not evaluated or unevaluable; PD=progressive disease; PR=partial response; SD=stable disease.

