9.10.6. Sensitivity Analyses for Missing Data

The preponderance of missing data for the key secondary efficacy endpoints of Active ROM, PROMIS-PF, Worst Stiffness NRS, and EQ-VAS will be evaluated. If there is more than 10% of missing data at Week 25 in any of the endpoints, then the impact of the missing data will be explored for that endpoint and will include, but may not be limited to, the following analyses:

- Multiple imputation based on randomized treatment to mimic missing at random
- A Pattern Mixture Model approach where participants who discontinued treatment due to an adverse event on vimseltinib will be imputed based on the missing not at random assumption and be imputed as if they received placebo.

In any exploration of missing data impact where a seed is required, the seed will be set to 20230428.

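### SAP 9.10.3 tests four key secondary endpoints with a sandwich variance but states no small-sample correction, degrees of freedom or reference distribution; read plainly, each test runs slightly above 5%

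*SAP*

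**What the plan says.** SAP 9.10.3 sets one model for the four continuous key secondary endpoints. It is a repeated-measures mixed model for change from baseline, fitted "using the sandwich estimator to estimate the variance-covariance matrix". Fixed effects are treatment, timepoint, their interaction, region, tumor location and the baseline value; for ROM, a three-level joint type replaces tumor location. The working covariance is unstructured, and the treatment comparison is a contrast at Week 25. For non-convergence the SAP says: "If the unstructured variance-covariance matrix fails to converge, then alternative structures will be utilized". It neither lists nor orders those structures.

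The ROM model has two timepoints (SAP 9.10.3.2). The PROMIS-PF, Worst Stiffness and EQ-VAS models have six (SAP 9.10.3.3 to 9.10.3.5).

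On implementation, SAP Section 9 says only: "All summaries and statistical analysis will be performed using SAS v9.4 or higher". It names no procedure or option, so no software default is fixed. Protocol 12.4.5.2 also specifies an unstructured covariance and does not mention a sandwich estimator.

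SAP 9.10.1 places these endpoints at steps 3 to 6 of a fixed sequence. After a failed step, "all subsequent endpoints will not be formally tested and nominal p-values will be provided".

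**The concern.** The uncorrected sandwich builds its variance from fitted residuals, which are smaller on average than the true errors. The bias is negligible in large trials. Here the smaller arm has about 40 participants, and about 34 at Week 25 after the planned dropout. A normal reference makes the test more liberal still, because it ignores the uncertainty in the estimated variance.

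These are confirmatory tests, so their p-value rule belongs in the plan. Nothing else in the SAP would expose the problem. For the primary endpoint, SAP 9.10.2 adds Fisher's exact test, and "an exact 95% CI for the difference in proportion will be provided as a sensitivity analysis". The sensitivity section written for the four continuous endpoints, SAP 9.10.6, deals only with missing data: above 10% missing at Week 25, "the impact of the missing data will be explored for that endpoint". No planned analysis checks the variance estimator or the reference distribution.

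**Working it through.** **Inputs from the documents.** About 80 versus 40 participants, "assuming 15% participant dropout" (SAP 5); two-sided alpha 0.05 (SAP 9.10.1); model terms and timepoints as above. At Week 25: 80 × 0.85 = 68 and 40 × 0.85 = 34.

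**The plan's own figure.** The only stated power is 98% for ORR of 35% versus 5%. Exact enumeration of the two-sided Fisher test at 80 versus 40 gives 98.3%, so it reproduces. The plan gives no power, SD or degrees of freedom for the four continuous endpoints, so there is no figure of that kind to check.

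**Size of the bias by hand.** Treat Week 25 as a single analysis of covariance. An uncorrected sandwich shrinks each participant's variance contribution by about (1 − h), where h ≈ 1/(arm size) + c/N and c counts covariate parameters besides intercept and treatment. For ROM, c = 4 (region, two for joint type, baseline); for the PRO models, c = 3. The contrast variance is about one third from vimseltinib and two thirds from placebo.

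- ROM, 68 versus 34: h = 1/68 + 4/102 = 0.054 and 1/34 + 4/102 = 0.069. Variance ratio = 1 − (0.054/3 + 2 × 0.069/3) = 0.936; SE ratio = √0.936 = 0.968.
- PRO, 68 versus 34: h = 0.044 and 0.059; variance ratio 0.946; SE ratio 0.973.
- No dropout, 80 versus 40: SE ratios 0.973 (ROM) and 0.977 (PRO).

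This agrees with the simulated ratio of mean SE to true SE over the ten settings below: 0.969-0.982 uncorrected, and 0.986-1.001 with Kauermann-Carroll.

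**What that does to the test.** Critical values are 1.960 (normal) and 1.983 (t, 105 df). At the middle of the uncorrected range, 1.960 × 0.9755 = 1.912, with two-sided tail 5.6%; 1.983 × 0.9755 = 1.934, with tail 5.3%. The simulated rates are a little higher because the estimated SE also varies from trial to trial.

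**Simulation of the full model with no treatment effect.** REML, unstructured covariance, 80 versus 40. ROM: 30,000 trials per setting (Monte Carlo SE 0.13 points). PRO: 20,000 (0.16 points). Type I error in %:

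| Setting | Uncorrected, normal | Uncorrected, t | Kauermann-Carroll, t |
|---|---|---|---|
| ROM, 15% dropout, corr 0.6 | 5.84 | 5.51 | 5.00 |
| ROM, no dropout | 5.79 | 5.58 | 5.17 |
| ROM, corr 0.3 | 6.31 | 6.00 | 5.42 |
| ROM, corr 0.8 | 5.81 | 5.55 | 5.00 |
| ROM, placebo SD × 1.3 | 6.39 | 6.07 | 5.46 |
| ROM, vimseltinib SD × 1.3 | 5.66 | 5.38 | 4.91 |
| PRO, decaying corr | 6.02 | 5.71 | 5.24 |
| PRO, constant corr 0.4 | 5.87 | 5.54 | 5.23 |
| PRO, placebo SD × 1.3 | 5.96 | 5.71 | 5.24 |
| PRO, vimseltinib SD × 1.3 | 5.83 | 5.57 | 5.18 |

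Here t is on between-subject degrees of freedom. Two further simulations agree:

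- Five settings of 4,000 trials, with other correlations and SD ratios: uncorrected 5.5-6.1% (normal) and 5.35-5.9% (t).
- The ROM model in three batches of 8,000: uncorrected 5.7-6.1% (normal) and 5.5-5.8% (t); Kauermann-Carroll with t, 4.8-5.3%.

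**Fallback covariance.** Under compound symmetry, with an assumed SD rising from 0.9 to 1.15 over visits, the rates are 5.5-6.1% (uncorrected, t) and 5.0-5.5% (Kauermann-Carroll, t). Model-based inference gives 7.4-8.3% there even with equal arm SDs.

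**Power cost.** For a true effect of 2.80 SEs and mid-range SE ratios, power is Φ(2.80 − 1.960 × 0.9755) = Φ(0.888) = 81.3% uncorrected with a normal reference. With Kauermann-Carroll and t it is Φ(2.80 − 1.983 × 0.9935) = Φ(0.830) = 79.7%. The loss is 1.6 points; the simulations give 1.5-1.9.

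**The case against.** **The effect is small.** This stands. Going from uncorrected t to Kauermann-Carroll t lowers type I error by 0.31-0.61 points in the table. If the uncorrected estimator is taken as given, normal versus t moves it by only 0.21-0.33 points. The case rests on stating the rule for confirmatory tests and on a cheap improvement.

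**A reader might infer that verdicts would often turn on an option picked late.** The documents do not support that. Naming the sandwich without a correction points to the uncorrected form, so bias-corrected forms are improvements, not rival readings. Between the two natural references, a statistic of 2.00 gives p = 0.046 (normal) and 0.048 (t, 105 df), which is the same verdict. Making it cross 0.05 takes a correction the SAP does not mention, or a reference such as 39 df that appears in neither document. Nor does anything show that the option would be chosen with results in view: SAP 6 bars aggregate analyses by true treatment before full unblinding, apart from permitted cases such as data monitoring committee review.

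**A reader might infer that the sandwich itself is the fault.** It is not. Model-based inference holds 4.9-5.3% with equal arm SDs. With an assumed SD ratio of 1.3 it gives 7.1-7.5% or 3.2-3.4%, depending on which arm varies more. The SAP chose the more robust estimator.

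**Other planned analyses support these endpoints.** The SAP plans MCID responder analyses for three of them, possible per-protocol repeats, and passive and contralateral ROM. These add evidence but do not settle how the confirmatory p-value is computed. The comparison with the primary endpoint's exact methods is also limited, since sparse binary data raise a different problem.

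**SAP Section 11.** It does not list the sandwich as a difference from Protocol 12.4.5.2. That is housekeeping and adds no weight here.

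**Conclusion.** The gap is real and worth closing, but its effect is modest. Read plainly, SAP 9.10.3 gives each of the four tests a simulated type I error of about 5.4-6.1% with a between-subject t reference, or 5.5-6.4% with a normal one, against a nominal 5%.

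The excess does not accumulate. In a fixed sequence, any false rejection requires rejecting the first true null hypothesis, so the familywise error cannot exceed the size of that one test. The Cochran-Mantel-Haenszel tests (RECIST ORR, TVS ORR, BPI-30) keep their own size; BPI-30 is touched only in that it is reached through steps 3 to 6.

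The figures assume normal data; the correlations and SDs shown; covariate splits in the main simulation of 30/70 (region), 80/20 (location) and 60/20/20 (joint type); and dropout unrelated to outcome, spread evenly over visits. None of these is in the documents. The direction and rough size hold across all settings tried and match the leverage arithmetic, which needs only the sample sizes and model terms.

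**What to change.** Keep the sandwich. Add to SAP 9.10.3 that inference on the Week 25 contrast, including under any fallback covariance structure, uses the Kauermann-Carroll bias-corrected sandwich with a t reference. Set the degrees of freedom to the number of participants with post-baseline data minus the number of between-subject parameters. Those parameters are intercept, treatment, region, tumor location or joint type, and baseline: five in the PRO models and six in the ROM model. If all 120 contribute, that is 115 and 114.

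Simulated type I error is then about 4.8-5.5%. Model-based inference, as Protocol 12.4.5.2 would suggest, can stay as a sensitivity analysis.

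The cost is one sentence and a programming option. Standard errors are about 2% larger (1.7-2.4% in the simulations), and power at 80% falls by about 1.5-1.9 points compared with the uncorrected normal-reference reading. As housekeeping, the sandwich estimator can be listed in SAP Section 11.

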6. RANDOMIZATION AND BLINDING

The study will randomize approximately 120 participants with TGCT in a 2:1 ratio (vimseltinib:placebo). Randomization will be stratified for tumor location (lower limb vs. all other) and region (U.S. vs. non-U.S.).

The present document, a comprehensive statistical analysis plan (SAP), will be approved by the Sponsor prior to the unblinding of study data.

Where required, safety personnel at the Sponsor or designee may be unblinded to a participant's study drug assignment to meet reporting requirements to regulatory agencies. In addition, the Investigator, participant, Sponsor, and study team will be unblinded at the time the participant has disease progression by RECIST v1.1 based on IRR.

Additional Sponsor representatives may be unblinded to some data for the purposes of ensuring adequacy of study conduct, including proper distribution of study drug.

At no point in time before official full study unblinding for the primary analysis will any aggregate efficacy and safety analyses by true treatment assignment be conducted by the Sponsor or Sponsor representatives, unless there is explicit permission to do so, for instance high level efficacy assessment for the purposes of a data monitoring committee (DMC) review to determine the adequacy of the risk/benefit profile of the drug as it pertains to the conduct of the clinical study.

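### The ROM model keeps the tumor-location stratum only in part, because the 'other' joint-type level can mix lower- and upper-limb joints; adding the stratum back is a free improvement

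*SAP*

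**What the plan says.** SAP 6 sets the design: "Randomization will be stratified for tumor location (lower limb vs. all other) and region (U.S. vs. non-U.S". Protocol 9.4 and 12.2 agree.

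SAP 9.10.3 gives a common mixed model for repeated measurements (MMRM) for the continuous key secondary endpoints, with both stratification factors and the baseline value as covariates. It then makes one exception: "For the analysis of ROM only, tumor location will be replaced with joint type (knee, ankle, or other". Protocol 12.4.5.2 makes the same exception. Region and baseline ROM stay in the model.

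ROM is tested as "3. Mean change from baseline in active ROM at Week 25", in a sequence run in the "following order at a 2-sided 0.05 alpha level for each" (SAP 9.10.1). The other six tests keep both factors. The RECIST, TVS and BPI-30 comparisons use a Cochran-Mantel-Haenszel test stratified as randomized, and the PROMIS-PF, Worst Stiffness and EQ-VAS models include tumor location.

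Neither document lists the joints in 'other', gives a reason for the replacement, or plans a supportive ROM model containing the stratum. The ROM forest plot has a tumor-location subgroup (SAP 9.10.3.2 and 9.10.5) but is not adjusted for the stratification factors. SAP 9.10.6 covers missing data only.

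**The concern.** The usual practice is to keep in the model the factors used to balance the arms. If a balanced factor predicts outcome and is left out, its variation stays in the residual. The computed standard error is then larger than the design warrants, and the test is a little conservative.

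Here the omission is partial. Knee and ankle each have their own level and both are lower limb. The remaining level can mix limbs: SAP 9.10.5 names hip, shoulder and elbow, Protocol Appendix 6 adds wrist and foot, and Protocol 11.9.15.1 mentions digits. Whether foot is coded with ankle is not stated.

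What is at stake is some precision at the third step of a fixed sequence. If ROM misses significance, PROMIS-PF, Worst Stiffness, EQ-VAS and BPI-30 are not formally tested. No power is stated for ROM, so the margin available is unknown.

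**Working it through.** **1. The plan's own figure.** SAP 5 states: "This sample size will have 98% power to detect a statistically significant difference between treatment groups". Behind that figure lie response rates of 35% on vimseltinib and 5% on placebo, and a total of "approximately 120 participants with TGCT (n~80 vimseltinib, n~40 placebo". Summing Bin(x; 80, 0.35) × Bin(y; 40, 0.05) over all tables with two-sided Fisher p ≤ 0.05 gives 0.983; a normal approximation gives 0.984. The figure reproduces. Applying "assuming 15% participant dropout" leaves 68 and 34 participants, and power is 0.963 (Fisher) or 0.961 (normal). All of this concerns response rate. The documents give no ROM effect, SD or power, so the steps below rest on assumptions.

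**2. How much of the stratum joint type retains.** Let L and U be the proportions of all participants who are in 'other' with a lower-limb and an upper-limb joint. The share of tumor-location variance captured by joint type is 1 − [LU/(L+U)] / [U(1−U)].

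| Assumed mix (knee / ankle / L / U) | Calculation | Captured |
|---|---|---|
| A: 65 / 12 / 12 / 11% | 1 − 0.0574/0.0979 | 41% |
| B: 65 / 12 / 4 / 19% | 1 − 0.0330/0.1539 | 79% |
| C: 50 / 10 / 25 / 15% | 1 − 0.0938/0.1275 | 27% (26.5%) |

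If 'other' held no lower-limb joints (L = 0), the stratum would be retained in full.

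**3. Effect on the standard error.** Let s be the share of participants in 'other', q the upper-limb fraction within it, and d the limb difference in mean ROM change in SD units. The residual variance explained by restoring the stratum is R = s·q(1−q)·d², and the SE falls by 1 − √(1−R).

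- s = 0.20, q = 0.5, d = 0.5: R = 0.20 × 0.25 × 0.25 = 0.0125; SE falls 0.6%.
- s = 0.30, q = 0.5, d = 1: R = 0.30 × 0.25 × 1 = 0.075; SE falls 3.8%.
- With a 90/10 split, q(1−q) = 0.09. The same two cases give R = 0.0045 and 0.027, and SE falls 0.2% and 1.4%.
- Mix C lies outside the 20% to 30% range, with s = 0.40. At d = 1, R = 0.40 × 0.625 × 0.375 = 0.094; SE falls 4.8%.

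**4. Simulation.** 120 participants were randomized 2:1 in blocks within location by region (30% U.S. assumed). Analysis was by linear model at one timepoint, with 6,000 runs under the null and 3,000 with a treatment effect of 0.6 SD. All models included region and were fitted to the same simulated data.

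| Mix, location gap | Type I: joint type | Type I: both | Power: joint type | Power: both | Change (points) |
|---|---|---|---|---|---|
| A, 0.5 SD | 0.051 | 0.052 | 0.854 | 0.856 | +0.2 |
| A, 1 SD | 0.044 | 0.047 | 0.847 | 0.860 | +1.3 |
| B, 0.5 SD | 0.049 | 0.051 | 0.862 | 0.861 | -0.1 |
| B, 1 SD | 0.055 | 0.059 | 0.844 | 0.853 | +0.9 |
| C, 0.5 SD | 0.055 | 0.055 | 0.857 | 0.862 | +0.5 |
| C, 1 SD | 0.044 | 0.049 | 0.847 | 0.868 | +2.0 |

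The Monte Carlo half-width for type I error is 1.96 × √(0.05 × 0.95/6000), about 0.006. In these two models the mean estimate ran from -0.007 to 0.004 when the truth was 0, and from 0.594 to 0.604 when it was 0.6, so neither shows bias.

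The simulation simplifies the planned analysis: it has no repeated measures, sandwich variance, baseline ROM or dropout. It also assumes no knee-ankle difference, so it cannot show what joint type contributes. It is no argument for removing joint type.

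**The case against.** The strongest case against is that this is a covariate preference. The choice appears identically in Protocol 12.4.5.2 and SAP 9.10.3. ROM is measured per joint, on the most impaired motion, and normalized to a motion-specific reference, so a joint-level covariate is plausible even though the documents do not give this reason. For knee and ankle, joint type carries the stratum and refines it. Any error in the SE works against the sponsor. The content of 'other' is inferred from other sections. The sizes depend on assumed inputs, and the 50/50 split maximizes them. Baseline ROM and normalization may already absorb some of the difference between limbs.

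All of that stands, and it limits the point to a small gain in precision. It does not remove the point, because joint type can stay while the stratum is added. A sound reason for including joint type is not a reason to leave out the randomization factor. The forest plot is no substitute, because it is unadjusted.

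A reader might infer more, without support from the documents:

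- *The ROM test ignores the randomization.* It does not. Region stays, and location is lost only inside 'other'.
- *ROM is not analysed as randomized.* That phrase normally refers to treatment arm, and SAP 7.2 analyses the ITT Set by allocated regimen.
- *The two documents disagree, or the covariate was changed late.* The Protocol and SAP carry the same rule.

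**Conclusion.** The ROM model retains the tumor-location stratum only in part, and it is the only model in the testing sequence to do so. The treatment estimate is unbiased. Type I error with joint type alone was 0.044 to 0.055 in simulation, so nothing suggests inflation, and the confirmatory status of ROM is not in question.

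The cost is a standard error that is slightly too large. Restoring the stratum cuts it by 0.2% to 3.8% with 20% to 30% of participants in 'other', a limb difference of 0.5 to 1 SD and a limb split between 90/10 and 50/50. It would be somewhat more if 'other' were larger. In power this is about 0 to 2 points. The joint mix, limb difference, region share and treatment effect are all assumptions.

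The position of ROM in the sequence might suggest that the endpoints after it are at risk. At this size the effect matters only for a borderline result. The point is a free improvement, not the correction of an error.

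**What to change.** Keep joint type and add tumor location (lower limb vs all other) to the ROM MMRM. Because knee and ankle are entirely lower limb, this is the same model as splitting 'other' by limb, provided the stratum is coded from the actual joint. The cost is one degree of freedom. The data are already planned: tumor location is a stratification factor, and the primary affected joint is summarized under SAP 9.5.

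Also list which joints fall in 'other', say where the foot belongs, and give the reason for using joint type.

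Make the change before unblinding and record it in SAP 11, since SAP 1 requires differences from the Protocol to be highlighted there. If the main model is to stay as it is, pre-specify the two-factor model as a supportive ROM analysis. That leaves the confirmatory test unchanged but does not recover the precision in it.
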